5 ENDPOINTS AND COVARIATES

Primary Endpoints-

1. To summarize the demographic and clinical characteristics.
Demographic characteristics will include

PFIZER CONFIDENTIAL

- Year of initial, metastatic and AMBC diagnoses;
- age at initial diagnosis, A/MBC diagnosis, start of palbociclib treatment and death;
- sex;
- race;
- ethnicity
- insurance status;
- menopausal status;
- region of residence at A/MBC diagnosis.

Clinical characteristics will include

[figure not shown]
- stage of initial diagnosis;
- histology;
- Eastern Cooperative Oncology Group (ECOG) performance status (where ECOG score unavailable, Karnofsky performance status will be converted to corresponding ECOG score);
- prior surgery (and type);
- prior radiation therapy (and type);
- comorbid disease burden (see Section 9.2);
- Charlson comorbidity index
- Sites of metastasis – visceral (liver, lung, peritoneum and pleural nodules), non-visceral, bone only
- Number of metastatic sites
 - Number of lesions in the site
 - Disease burden in the liver, lungs, bone
- time to metastasis (time between initial and metastatic diagnoses)
- HER2 and estrogen receptor (ER)/ progesterone receptor (PR) status;
- BRCA status
- modalities of treatment received prior to A/MBC diagnosis (chemotherapy, hormone therapy, surgery, radiation therapy);
 - Documentation of endocrine sensitivity and endocrine resistance if hormone therapy received in adjuvant setting
- disease free interval (time between completion of adjuvant therapy and diagnosis of A/MBC).

2. To summarize treatment patterns.

Treatment patterns will be evaluated by the review of

- the distribution of regimens;
- sequence of regimens across the lines;
- description of dosing which will include the starting dose, end dose, dose adjustment (dose increase and dose reduction), type of dose adjustment (dose modification, schedule changes, dose delay or hold), discontinuation reason (including death, progression, end of planned therapy, insurance changes, schedule change, dose delay, hold, cost, patient refusal, toxicity), and time to dose adjustment

PFIZER CONFIDENTIAL

[figure not shown]

3. To summarize the effectiveness outcomes of treatment-
 - a. Real-world progression-free survival (rwPFS) for the first-line therapy at time points 3, 6, 12, 18, 24, 30, and 36 months;
 - b. Real-world overall survival (rwOS) from the start of the first-line therapy at time points 6, 12, 18, 24, 30, and 36 months.
 - c. Real-world time to treatment discontinuation (rwTTD) from the start of the first-line therapy at time points 3, 6, 12, 18, 24, 30, and 36 months.
 - d. Real-world time to next treatment (rwTTNT) from the start of the first-line therapy at time points 3, 6, 12, 18, 24, 30, and 36 months.
 - e. Real-world time to chemotherapy (rwTTC) from the start of the first-line therapy at time points 3, 6, 12, 18, 24, 30, and 36 months.
 - f. Real-world time to dose adjustment (rwTTDA) from the start of the first-line therapy at time points 3, 6, 12, 18, 24, 30, and 36 months.

5.1 Definitions/Derivations for Demographic, Clinical characteristics, treatment pattern and Efficacy/Effectiveness Endpoint(s)

- Age at initial diagnosis, A/MBC diagnosis, at start of palbociclib treatment and death. - They will be categorized into age categories: <50, 50-64, 65 –74, ≥75 years.
- Time to metastasis- It is defined as months between initial and metastasis diagnoses. It will be categorized into ≤12 months, 13-24 months, 25-36 months,>36 months and de novo metastatic.
- Disease Free Interval (DFI)- It is defined as months from the end of adjuvant therapy to the date of disease recurrence. It will be categorized into ≤12 months, 13-24 months, 25-36 months,>36 months and Unknown.
- Line of therapy- The line number (1; 2; 3; etc.) in the A/MBC setting will be assigned based on Syapse line of therapy algorithm.
- Regimen medication(s)- Systemic therapies included in line regimen defined by Syapse line of therapy algorithm.
- Time to first dose change- It is defined as days from palbo dose 1 start date to palbo dose 2 start date, if applicable.
- Number of dose changes- Number of dose reduction(s) and number of dose increases over the calendar time (quarter since February 2015) and over treatment cycle since palbo dose 1 start date.
- Real-world Overall Survival (rwOS)- It is defined as length of time from the start of palbociclib + AI treatment to the earliest of the following: date of death, date of last contact, or the end of study period
- Real-world progression free survival (rwPFS)- It is defined as length of time from the start of palbociclib + AI treatment to the earliest of the following: clinician-assessed progression event (sources include medical oncology consult/note, radiation oncology note and discharge summary), date of death, date of initiation

PFIZER CONFIDENTIAL

of the 2nd line for patients with >1 line of therapy, date of last contact, or end of study period.

- Real world time to treatment discontinuation (rwTTD)- It is defined as length of time from the start of palbociclib + AI treatment to the earliest of the following: date the patient discontinues first-line treatment, date of death, last known usage of first-line treatment, or end of study period.
- Real world time to next treatment (rwTTNT)- It is defined as length of time from the start of palbociclib + AI treatment to the earliest of the following: subsequent line of therapy initiation, date of death, date of last contact, or end of the study period.
- Real world time to chemotherapy (rwTTC)- It is defined as length of time from the start of palbociclib + AI treatment to the earliest of the following: the day before the start of subsequent chemotherapy for patients with evidence of chemotherapy, or date of death for any reason. Or, where censored, the latest of date of last contact, or end of the study period.
- Real world time to dose adjustment (rwTTDA)- It is defined as length of time from the start of palbociclib + AI treatment to the earliest of the following: date of first-line treatment dose adjustment, date of death, date of first-line treatment discontinuation, date of last contact or end of study period.

5.2 Safety Endpoints

Not Applicable.

5.3 Other endpoints

Not Applicable.

6 HANDLING OF MISSING VALUES

In general, data that are absent/not found will not be imputed but will be categorized and reported as not documented.

7 STATISTICAL METHODOLOGY AND STATISTICAL ANALYSES

7.1 Statistical methods

Descriptive analyses: For categorical variables (eg region, race, and stage at initial diagnosis), data will include the frequency (number of cases) and percentage (%) of total patients observed in each category; for continuous variables (eg age and time from initial breast cancer diagnosis to metastatic diagnosis), variables will be presented as the mean, standard deviation (SD), median, 25th and 75th percentiles and ranges (minimum and maximum) in some cases. The calculation of percentages will always include the missing category in the case of missing values. Continuous variables may be categorized into intervals, with the distribution of patients (N, %) provided.

Kaplan-Meier curves and landmark analyses will be performed to estimate rwPFS, rwOS, rwTTD, rwTTC, rwTTDA and rwTTNT. Specifically, landmark time points are; 3, 6, 12, 18, 24, 30, and 36 months for rwPFS and 6, 12, 18, 24, 30, and 36 months for rwOS. For rwTTD and rwTTNT, landmark time points are; 3, 6, 12, 18, 24, 30, and 36 months. Ninety-five percent confidence intervals on the median rwPFS, rwOS, rwTTD, rwTTNT, rwTTC and rwTTDA will be reported.

Cox proportional hazard models may include age categories, race, ECOG performance, menopausal status, stage at initial diagnosis, time from initial diagnosis to metastatic diagnosis, metastatic status (De novo, versus number of metastatic sites), number of disease sites (1, 2, ≥ 3), prior endocrine therapy, prior chemotherapy, prior surgery, prior radiation therapy, bone-only disease, presence of visceral disease, and presence of brain metastases as appropriate based on availabilities of the data and sample sizes. Potential interactions may be examined using survival trees for time to events.

All data analysis will be executed using statistical software R version 3.6.1 or later.

7.2 Statistical Analyses

Objective1:

- a. To describe the demographic and clinical characteristics for patients diagnosed with HR+/HER2- A/MBC.

[figure not shown]
The numbers of breast cancer patients in the Syapse database meeting the eligibility criteria will be presented in an attrition table.

Demographic and clinical characteristics variables that will be reported include age, sex, race, insurance status, menopausal status, and region of residence at A/MBC diagnosis, stage of initial diagnosis, histology, Eastern Cooperative Oncology Group (ECOG) performance status (where ECOG score unavailable, Karnofsky performance status will be converted to corresponding ECOG score) and comorbid disease burden, HER2 and estrogen receptor (ER)/ progesterone receptor (PR) status, BRCA status, number and sites of distant metastasis at A/MBC diagnosis; modalities of treatment received prior to A/MBC diagnosis (chemotherapy, hormone therapy, surgery, radiation therapy), disease free interval (time between completion of adjuvant therapy and diagnosis of A/MBC) and follow-up time in the study. Descriptive analysis methods as detailed in Section 7.1 will be used for summarizing these parameters as appropriate.

- b. To describe the treatment patterns for patients diagnosed with HR+/HER2- A/MBC.

Treatment patterns generally include the record of all systemic anti-cancer therapies received from the index date through the end of the study period.

CCI

Description will include each of the following.

- Distribution of regimens, with the frequency and percentage of patients receiving each regimen within each line from the diagnosis of A/MBC through the end of the record.
- Description of sequence of regimens across lines, which shows how individual regimens were sequenced across lines through the end of the record of systemic therapy. Description will include the frequency and percentage of patients who received each specific sequence of treatments.
- Description of the dosing will include the starting dose, end dose, dose adjustment (dose increase and dose reduction), type of dose adjustment (dose modification, schedule changes, dose delay or hold), discontinuation reason (including death, progression, end of planned therapy, insurance changes, schedule change, dose delay, hold, cost, patient refusal, toxicity), and time to dose adjustment.

Objective2:

To examine clinical effectiveness for patients diagnosed with HR+/HER2- A/MBC.

Kaplan-Meier survival analysis is used to descriptively characterize time to event outcomes. In this study, following time to event outcomes will be analyzed-

- Time to Real-world overall survival (rwOS)

[figure not shown]
The time origin for analysis of rwOS is start of the first-line therapy, and the terminal event is death. For patients not known to be deceased at the time of analysis, rwOS will be censored at the earliest of the last date of last contact or the end of the study period.

- Time to Real-world progression-free survival (rwPFS)

The time origin for analysis of rwPFS is start of the first-line therapy. Patients without a clinician-assessed progression event or death will be censored at the earliest of the following events: date of initiation of the 2nd line for patients with >1 line of therapy, date of last contact, or end of study period.

- Real world time to treatment discontinuation (rwTTD)

PFIZER CONFIDENTIAL

The time origin for analysis of rwTTD is start of the first-line therapy. Patients without first-line treatment discontinuation and who did not die will be censored at the earliest of the following events: last known usage of first-line treatment, or end of study period.

- Real world time to next treatment (rwTTNT)

The time origin for analysis of rwTTNT is start of the first-line therapy. Patients without a subsequent line of therapy initiation and who did not die will be censored at the earliest of the following events: date of last contact, or end of the study period.

- Real world time to chemotherapy (rwTTC)

The time origin for analysis of rwTTC is start of the first-line therapy. Patients who did not receive subsequent chemotherapy and who did not die will be censored at the latest of the following events: date of last contact, or end of the study period.

- Real world time to dose adjustment (rwTTDA)

The time origin for analysis of rwTTDA is start of the first-line therapy. Patients without a first-line treatment dose adjustment will be censored at the earliest of the following events: first-line treatment discontinuation, date of death, date of last contact, or end of the study period.

One Kaplan-Meier analysis is generated for each time to event endpoint. Kaplan-Meier analysis will include number of patients with events and censored patients, median, 25th percentile and 75th percentile times to event (in months), 95% CI of the quartiles and ranges (minimum and maximum). Kaplan-Meier analysis will be repeated in the subgroup of patients who received a starting dose of 125mg.

One Cox regression analysis will be generated for each time to event endpoint, provided the sample size supports the analysis. Demographic and baseline clinical characteristics, some examples are detailed in section 7.1, will be included to the extent that sample size permits. Results from this analysis results will include parameter estimates, p-values, standard errors, hazard ratios and 95 % CIs of hazard ratios. The proportional hazards assumption will be assessed graphically with the inspection of Schoenfeld residuals and by including interaction terms between the variables and log(time).

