2.1 Study Design

[figure not shown]
This is an observational, retrospective cohort study. Eligible patients will be identified from the Syapse Learning Health Network database and medical chart review will be conducted by Syapse Certified Tumor Registrars (CTRs). All study data are secondary data and will have been collected retrospectively from existing clinical data originally collected as part of routine care. This single-arm descriptive analysis will describe the patient characteristics, clinical attributes and treatment patterns of A/MBC patients with HR+/HER2- disease, who were treated with palbociclib + AI as first-line therapy. Additionally, clinical effectiveness outcomes for these patients will be evaluated between Feb 2015 and July 2019.

Study population

The study will include adult patients 18 years or older, diagnosed with HR+/HER2- A/MBC who initiated palbociclib combination therapy with AI as the first-line therapy on or after 03 February 2015 up to and including 31 July 2019. Patients for this study will be identified from the Syapse Learning Health Network database.

Preliminary analysis identified up to 1,074 patients with evidence of key primary inclusion criteria: breast cancer diagnosis and palbociclib treatment. Three to four hundred patients are expected to fulfil complete study inclusion criteria. Given the inclusion criterion requiring a qualifying treatment identification period between 03 February 2015 through 31 July 2019, and assuming a data cutoff date of 01 February 2020, the minimum follow-up available is therefore 6 months.

PFIZER CONFIDENTIAL

Data source

Patients will be identified and data will come from the Syapse Learning Health Network database which includes both inpatient and outpatient clinical and molecular data captured through manual abstraction and interoperative data feeds from a number of health system source systems, including:

- *Electronic medical record (EMR), including inpatient, outpatient oncology, ambulatory, surgical, etc.*
- *Electronic data warehouse (EDW)*
- *Laboratory information system (LIS)*
- *Picture archiving and communication system (PACS)*
- *Hospital based cancer registries*
- *Computerized physician order entry (CPOE)*

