- *Additionally, Syapse augments health system data with the Surveillance, Epidemiology, and End Results (SEER) national cancer registry, other regional registries, the Social Security Death Index (SSDI), digitized obituary data. In order to capture complete and accurate vital status and dates of death, Syapse brings together data from multiple sources to create a composite view of patients' mortality (including EHR, hospital registry, manual abstraction, digital obituaries (such as tributes.com and legacy.com), Social Security Death Index, and SEER). Syapse is in the process of validating the completeness and accuracy of the Syapse mortality composite score versus the National Death Index (NDI), a centralized database of death records. Initial analysis shows that the combined Syapse Data Sources are very accurate. More detailed information forthcoming in the data management document.*

Treatment/cohort labels

Data from patients with only one treatment group labelled as palbociclib + AI are explored in this retrospective study.

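### rwOS time stops at the end of the study period but event status follows vital status at analysis, so deaths dated after that end can be counted as events

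*SAP*

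**What the plan says.** Section 5.1 defines rwOS as time from the start of palbociclib plus AI "to the earliest of the following: date of death, date of last contact, or the end of study period". Appendix 2 (Section 9.2) repeats this. Neither place says which of these endings is an event and which is a censoring.

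Section 7.2 supplies the status: "The time origin for analysis of rwOS is start of the first-line therapy, and the terminal event is death". Its censoring rule then reads: "For patients not known to be deceased at the time of analysis, rwOS will be censored at the earliest of the last date" of contact or the end of the study period. The rule covers only patients not known to be dead at analysis.

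The other endpoints that count death use similarly undated wording. For rwTTD: "Patients without first-line treatment discontinuation and who did not die will be censored at the earliest of the following events". The rwPFS, rwTTNT and rwTTC rules also refer to death without a date limit. rwTTC differs further, because it censors at the latest, not the earliest, of last contact and end of study period.

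On the end of the period, Section 2.1 says effectiveness outcomes are evaluated from February 2015 to July 2019. It also gives a cutoff: "assuming a data cutoff date of 01 February 2020, the minimum follow-up available is therefore 6 months". On deaths, the same section says the data provider "brings together data from multiple sources to create a composite view" of mortality and lists several sources, with no date limit on the deaths taken from them. Appendix 2 captures last contact only for patients who are alive.

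**The concern.** Time and status are tied to different dates: time to the end of the study period, status to the time of analysis. A patient who dies between the two has no written censoring rule. Taking time from 5.1 and status from 7.2 gives a death on the last day of the period. Taking 7.2 alone gives a death at its true date, beyond the period. In both cases follow-up past the end is credited only to those who die, while comparable survivors are censored at the end or earlier. That is outcome-dependent censoring, and it pulls the Kaplan-Meier curve down. In a single-arm descriptive study the rwOS median and landmarks are themselves the result, and no comparator absorbs the error.

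**Working it through.** **The plan's own figure.** From 31 July 2019 to 01 February 2020 is 185 days; 185 / 30.44 = 6.08 months. The stated six-month minimum follow-up is reproduced, and it fits 01 February 2020 as the end.

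**Inputs from the SAP.** Index window 03 February 2015 to 31 July 2019, W = 53.8 months. Follow-up to the end of the period runs from a to b = a + W. With a 01 February 2020 end, a = 6.08 and b = 59.88. With a 31 July 2019 end, a = 0 and b = 53.8. Expected sample size is 300–400.

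**Assumptions not in the SAP.** Uniform entry, exponential survival with hazard λ = ln 2 / median, no other loss, and deaths known for k months past the end.

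**Three codings of a later death.**
- A: censored at the end of the period. This recovers the true curve.
- B: event at the true date of death.
- C: event at the end of the period.

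**Rule C in closed form.** Let p = 1 − exp(−λk), the chance that a patient alive at the end dies within k months. With uniform entry, the hazard beyond month a becomes λ + p/(b − t), so for t > a

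S_C(t) = exp(−λt) × [(b − t)/W]^p.

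Median 40, k = 6, end 01 February 2020: λ = 0.01733 and p = 0.09875. At 36 months the true value is 0.5359, and (59.88 − 36)/53.8 = 0.4439. So S_C = 0.5359 × 0.4439^0.09875 = 0.5359 × 0.9229 = 0.495.

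Median 48: p = 0.0830, so S_C = 0.5946 × 0.4439^0.0830 = 0.5946 × 0.9348 = 0.556.

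End 31 July 2019, median 40: (53.8 − 36)/53.8 = 0.3309, so S_C = 0.5359 × 0.3309^0.09875 = 0.480.

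**Rule B.** With G(t) the share of patients whose follow-up to the end is at least t, the hazard is

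λ S(t) G(t − k) / { S(t) G(t) + (1/W) ∫ [S(t) − S(f + k)] df }, with f from max(a, t − k) to min(t, b).

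At month 36 in the first scenario this is 0.2976λ / (0.2379 + 0.0030) = 1.24λ. Integrated numerically:

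| End of period | True median (mo) | k (mo) | True 36-mo rwOS | Rule B | Rule C | Estimated median (B; C) |
|---|---|---|---|---|---|---|
| 01 Feb 2020 | 40 | 0 | 53.6% | 53.6% | 53.6% | 40; 40 |
| 01 Feb 2020 | 40 | 3 | 53.6% | 51.5% | 51.4% | 37.5; 37.4 |
| 01 Feb 2020 | 40 | 6 | 53.6% | 49.8% | 49.5% | 35.8; 35.5 |
| 01 Feb 2020 | 40 | 12 | 53.6% | 47.3% | 46.0% | 33.7; 32.6 |
| 01 Feb 2020 | 48 | 6 | 59.5% | 55.9% | 55.6% | about 42 |
| 31 Jul 2019 | 40 | 6 | 53.6% | 48.4% | 48.0% | 34.5; 34.2 |

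Large simulations agree to within about 0.2 points (for example 49.4–49.7% in the third row).

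**Number of patients.** The share dying within k months after the end is p × [exp(−λa) − exp(−λb)] / (λW) = 0.09875 × (0.9000 − 0.3543) / 0.9323 = 5.8%, or about 17–23 of 300–400 (median 40, k = 6, end 01 February 2020).

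**Scale.** At n = 350 and median 48, the standard error of 36-month rwOS is about 3.2 points. The six-month shift of 3.6–3.9 points is 1.1–1.2 standard errors.

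**Landmarks.** With the 01 February 2020 end, a exceeds 6 months, so 6-month rwOS is 90.1% under all three codings (median 40). At 12 months with k = 6 it moves from 81.2% to 80.3–80.8%. With a July 2019 end the 6-month landmark does move, from 90.1% to 89.1–89.6%.

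**The case against.** A reader might infer that the SAP does count post-cutoff deaths and that rwOS is therefore biased. The documents do not support that. No sentence says such deaths become events. Section 5.1 ends observation at the earliest of three dates, and for a later death that date is the end of the study period, so censoring there is a natural reading. Section 7.2 gives event status only by implication. Nor does the SAP say that deaths dated after the cutoff will be in the file: a data cutoff ordinarily bounds the data, and linking late to a death that occurred before the cutoff is correct ascertainment. With no later deaths in the data, the bias is zero. The July 2019 date may be only a loose restatement of the index window.

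Two further extensions also fail. The effect does not reach every landmark, since 6-month rwOS is untouched with a 01 February 2020 end. And although the undated wording recurs for rwPFS, rwTTD, rwTTNT and rwTTC, no size has been calculated there; patients who already had the non-death event are unaffected.

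What stands against this is that the unbiased reading is not written down. Capping last contact at the end of the study period has an effect only if records can run past that end, the mortality sources carry no date limit, and the two dates in Section 2.1 could by themselves produce a gap of about six months.

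**Conclusion.** The point holds as a gap in the event definition with a conditional bias. Sections 5.1 and 7.2 do not settle how to code a death after the end of the study period, and that end is not given as a single date. If such deaths are present and counted, the direction is always downward. Six months of them cost about 4 points of 36-month rwOS with a 01 February 2020 end, and about 5–6 points with a July 2019 end (median 40), alongside a median some 4–6 months too short. These sizes rest on the assumed exponential survival, true median, uniform entry, absence of other loss and length of the gap; none of these is in the SAP. The documents do not establish that any bias is present in the data.

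**What to change.** State one calendar date for the end of the study period and reconcile the two statements in Section 2.1 with it. In Section 7.2, count a death as an event only if it is dated on or before that date, for rwOS and for every other endpoint in which death is an event, and remove the reference to the time of analysis. For rwOS, censor patients who died later as patients alive on that date, at the earlier of their last contact and that date. Treat them the same way for the other endpoints, under each endpoint's own censoring dates. For rwTTC, whose current rule takes the latest date, write the censoring date out explicitly.

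The cost is modest but more than one line of code: last contact must also be derived for patients who later died, since Appendix 2 captures it only for the living, and a few later deaths go unused. Section 1 refers to a manuscript draft, so the data seem to be in hand; a count of deaths dated after the chosen end would show whether any reported figure can change.

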9.2 APPENDIX 2: Description of data elements used in the study

The following data elements will be extracted from feeds and/or curated by Certified Tumor Registrars (CTRs) for this study:

Data Elements	Description
Demographic characteristics	
Date of birth	Year, month, day (Availability of the exact date will depend on the Expert de-ID approach)
Date of initial BC diagnosis	Date of initial breast cancer (BC) diagnosis
Date of A/MBC diagnosis	Date of advanced/metastatic breast cancer (A/MBC) diagnosis
Patient sex	Male, Female, Transsexual, Other, Not Provided
Primary race	American Indian/Alaska Native; Asian; Black/African American/Native Hawaiian/Pacific Islander; White; Not Provided; Other (Exact list will depend on the expert de-ID approach)
Secondary race	(if provided) (Exact list will depend on the expert de-ID approach)
Ethnicity	Non-Hispanic/Non-Latino; Hispanic/Latino; Unknown (Exact list will depend on the expert de-ID approach)
Region of residence	Northeast, Midwest, South, West Captured at A/MBC diagnosis (Exact list will depend on the expert de-ID approach)
Insurance type	Medicare/Medicaid; Commercial; Commercial and Medicare/Medicaid; None; Not Provided Captured at 1) date of A/MBC diagnosis; and 2) at initiation of palbo
Menopause status	Premenopausal; Postmenopausal; Perimenopausal; Unknown; Not applicable. Captured on date closest to but before: 1) A/MBC diagnosis; and 2) initiation of palbo

PFIZER CONFIDENTIAL

	
Menopausal status: captured if explicitly stated in clinician notes. Otherwise captured based on following definition of menopause from NCCN Guideline v.3.2019:
 
Prior bilateral oophorectomy (date of surgery)
 
Age >=60 years old
 
Age <60 years old and amenorrheic for 12 months+ in the absence of chemotherapy, tamoxifen, toremifene, or ovarian suppression.
 
Additionally, type, name, and start/end date of ovarian suppression agent is captured

Date of death	If patient vital status = deceased, date of death from the medical record (capturing from EMR, registries, third party integrations) (Availability of the exact date will depend on the Expert de-ID approach)
Last contact date	If patient is alive (not deceased), date of the last contact by a healthcare provider from the medical record (Availability of the exact date will depend on the Expert de-ID approach)
Clinical characteristics	

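### rwOS counts deaths found outside the health system but censors everyone else at last provider contact, so censoring depends on outcome and no sensitivity analysis shows the effect

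*SAP*

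**What the plan says.** **Event and censoring.** For rwOS, SAP section 7.2 states: "The time origin for analysis of rwOS is start of the first-line therapy, and the terminal event is death". For patients not known to be dead, "rwOS will be censored at the earliest of the last date of last contact or the end of the study period".

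**Where the last-contact date comes from.** Section 9.2 defines it as: "If patient is alive (not deceased), date of the last contact by a healthcare provider from the medical record". It exists only for living patients and needs a provider contact.

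**Where death dates come from.** The same appendix gives "date of death from the medical record (capturing from EMR, registries, third party integrations" and section 2.1 names, among the sources, "digital obituaries (such as tributes.com and legacy.com), Social Security Death Index, and SEER". These can record a death with no further contact with the health system.

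**How good the death data are.** Section 2.1 says "Initial analysis shows that the combined Syapse Data Sources are very accurate", but also "Syapse is in the process of validating the completeness and accuracy of the Syapse mortality composite score versus the National Death Index (NDI". No sensitivity figure is given.

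**What is planned.** Section 7.2 plans one Kaplan-Meier and one Cox analysis per time-to-event endpoint, with Kaplan-Meier repeated for the 125 mg starting-dose subgroup. Neither section 7.2 nor the summary table in 7.2.2 includes a second censoring rule for rwOS. For rwTTC, section 7.2 censors at the later of last contact and end of study, the reverse of the rwOS rule, and does not explain the difference.

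**The concern.** Take two patients who leave the network at month 12. One dies at month 30 and is found through an obituary. That patient contributes 30 months at risk and one event. The other is alive at the data cutoff and contributes only 12 months. Both had the same contact history, and the later outcome alone decides whether the time after month 12 enters the risk set.

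Kaplan-Meier requires censoring to be unrelated to the event given survival so far. This rule breaks that requirement even when leaving care has nothing to do with prognosis. Section 5 lists rwOS among the primary endpoints, with landmarks to 36 months. The planned 95% confidence intervals describe sampling error and would not reveal a shift of this kind.

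**Working it through.** **1. The SAP's own figure.** Section 2.1 states a minimum follow-up of 6 months. From 31 July 2019 to 1 February 2020 is 185 days, and 185/30.4375 = 6.08 months, so it reproduces. The maximum, from 3 February 2015, is 1,824 days or 59.93 months. These are potential follow-up times; censoring at last contact can make a survivor's actual follow-up shorter.

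**2. Assumptions that are not in the SAP.** Exponential survival with true median 48 months, so hazard λ = ln 2/48 = 0.01444 per month and true 36-month survival 2^(-36/48) = 59.5%. Entry uniform over the SAP window. Loss of contact at 5, 10 or 15% per year, at first unrelated to prognosis. A fraction s of deaths after departure is captured.

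**3. Effect on the hazard.** Let G(t) be the probability of still being in contact at t. Let p(t) be the probability that a patient alive and within potential follow-up at t dies before the cutoff. Departed patients supply events in proportion s, but stay in the risk set only if they will later be a captured death, in proportion s·p. So

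apparent hazard / true hazard = [G + (1 − G)s] / [G + (1 − G)s·p].

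This equals 1 when s = 0 and exceeds 1 whenever s > 0, since p < 1. For t beyond 6.08 months, p(t) = 1 − [1 − exp(−λ(59.93 − t))] / [λ(59.93 − t)].

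Example at t = 36, 10% loss per year, s = 1:
- G = 0.9³ = 0.729
- λ × 23.93 = 0.3456, so p = 1 − (1 − 0.708)/0.3456 = 0.154
- ratio = 1/(0.729 + 0.271 × 0.154) = 1/0.771 = 1.30

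**4. Integrated over time.** Ranges run from 100% to 90% capture. Simulated Kaplan-Meier estimates agree to within about half a month.

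| Loss per year | Median, SAP rule | 36-month survival, SAP rule | Median, cutoff censoring (simulated) |
|---|---|---|---|
| 5% | 44.4-44.7 | 57.6-57.8% | about 48-49 |
| 10% | 41.5-41.9 | 55.5-55.9% | about 48-49.5 |
| 15% | 38.9-39.5 | 53.3-53.9% | about 48-50 |

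Against 59.5%, 36-month survival falls by 59.5 − 57.8 = 1.7 to 59.5 − 53.3 = 6.2 points. At 24 months (true 70.7%), full capture gives 69.8, 68.8 and 67.7%, a fall of about 1 to 3 points.

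**5. Visit spacing alone.** Suppose nobody leaves care but the last visit falls 0 to 3 months before the cutoff (mean 1.5). The excess cumulative hazard by month 46 is about λ × 1.5 × ln(53.8/13.9), equivalent to about 2 months. Simulation gives a median of 45.9.

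**6. When departure is prognostic.** Simulated medians at 10% loss per year, with the hazard multiplied after departure:

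| Hazard multiple | Capture | True | SAP rule | Cutoff censoring |
|---|---|---|---|---|
| 3 | 100% | 39.0 | 36.9 | 39.1 |
| 3 | 80% | 39.0 | 38.4 | 41.9 |
| 3 | 50% | 39.0 | 41.0 | 47.8 |
| 6 | 90% | 34.8 | 34.8 | 36.1 |
| 6 | 80% | 34.8 | 35.7 | 37.8 |

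The sign changes as capture falls, and in the third and fifth rows both estimates lie above the truth.

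**7. Cutoff censoring has its own failure.** If 10% of all deaths are missed at random, the estimated curve is 1 − 0.9F(t). It reaches one half when F = 0.556, that is S = 0.444, at 48 × log₂(1/0.444) = about 56 months against a true 48.

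**The case against.** The strongest reply has four parts.

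- **Direction is not established.** A reader might infer that rwOS is biased downward, full stop. The documents do not support that. The remark about accuracy in section 2.1 is qualified by an unfinished validation, and accuracy of recorded deaths is not the same as sensitivity after a patient leaves. This part stands.
- **Two analyses do not bound the truth.** A reader might infer that last-contact and cutoff censoring give a lower and an upper limit. The prognostic scenarios above show both on the same side of the truth. This part stands too.
- **The shift may be small beside the noise.** With 350 patients (section 2.1 expects 300 to 400), the standard error of 36-month survival is about 3.2 to 3.3 points, and the 95% sampling range of the median at 5% loss per year is about 37 to 54 months. A shift of 2 points or 3.5 months sits inside that. This is fair at low loss rates. At 10% per year the shift of about 4 points exceeds one standard error, and the planned intervals do not account for it.
- **The rule is consistent and the study descriptive.** The SAP states the rwOS rule consistently, tests no hypothesis, and will report follow-up times and censored counts. That is true, but those tables do not show how the estimate responds to the censoring date.

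A separate reading, that the definition in section 5.1 could censor a patient who died at last contact, also fails: section 9.2 gives that date only to living patients and section 7.2 makes death the event.

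**Conclusion.** The asymmetry is in the text and needs no assumption: deaths can be recorded without provider contact, survival time cannot, and no planned analysis varies the rwOS censoring date. Followed exactly, the rule makes censoring depend on outcome and can bias a primary endpoint.

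Direction and size are conditional. With non-prognostic departure the bias is downward at any capture level above zero. Under the assumed 48-month median and 90-100% capture it is roughly 3 to 9 months on the median for 5 to 15% annual loss. With strongly prognostic departure and incomplete capture it can vanish or reverse. None of these inputs is in the SAP, so the figures show what is possible and do not estimate the bias in this cohort. This is a worthwhile, inexpensive improvement and does not show that the primary rule must be replaced.

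**What to change.** Keep the current rule as primary if preferred. Add to section 7.2 one prespecified sensitivity Kaplan-Meier analysis of rwOS that censors patients not known dead at the data cutoff, or at the last date to which the composite mortality data are complete if that is earlier. State in the same place which date is used. Add the row to section 7.2.2 and a matching table and figure to section 8.2.1.

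Report the two estimates together with the National Death Index validation result, and label them a sensitivity pair. A wide gap tells the reader that the result hangs on death capture and loss of contact. A narrow gap means only that the choice between these two censoring dates matters little.

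The cost is one table and one figure from data already held, and two rwOS estimates to explain instead of one.
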